### **7.2.8 Partial/Missing Dates for Adverse Events**

For any adverse event that has a missing or incomplete start date, a query will be issued to capture the full date. If only a partial date is reported for the start of an AE, a complete date will be estimated using the following algorithm:

- If only the year is reported (i.e., missing the month and day): The date of the first dose of investigational product will be used as the start of the AE.
- The year and month are reported (i.e., missing the day): The first day of the month will be imputed.
- The month and day are reported (i.e., missing the year): only situations where the year is self-evident will be allowed.

No imputation will be applied to an incomplete AE end date. The rationale will be that there should be a start date for all subject AEs but there may not be an end dates for AEs that are ongoing at the time the subject exits the study.

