9.5.2 Analysis of Key Study Endpoints

9.5.2.1 Adverse Events

Each reported adverse event will be assigned a System Organ Class (SOC), a higher level group term, a high level term and a preferred term according to the current version of the Medical Dictionary for Drug Regulatory Activities (MedDRA). The severity of adverse events will be assigned in accordance with the NCI CTCAE version 4.03 guidelines.

All adverse events will be listed by subject. The subject incidence rate of adverse events occurring between informed consent and first dose of study drug will be summarized by system organ class and preferred term for the Safety Analysis Set.

The incidence rate of treatment emergent adverse events, defined as all adverse events reported as new or worsened after the start of study drug, will be summarized by treatment group, system organ class, preferred term and maximum severity (where appropriate) for all adverse events, serious adverse events, adverse events leading to discontinuation of study specified treatment, adverse events leading to discontinuation from the study and fatal adverse events using subjects in the safety population. In addition, summaries of exposure adjusted adverse event rates may also be presented. These summary tables will also be repeated for treatment related adverse events. The number and percent of subjects reporting adverse events (all, serious, and related) will be tabulated by dose levels. Narratives of all serious and fatal adverse events will also be provided.

A listing and summary of the incidence of dose limiting toxicities present will be reviewed to make dose escalation decisions in Stage 1 review (dose limiting toxicity assessment set) will also be produced by treatment group and by subject.

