### Dose-Limiting Toxicity (DLT)

The definition of DLT is described in Section 6.5 of this SAP. Dose-limiting toxicity will be evaluated during Cycle 1 of treatment. For purposes of displaying DLTs on a per-subject and per-cohort basis,

the Electronic Data Capture (EDC) system will capture and identify whether or not a subject experiences a DLT in the AE dataset.

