### **7.2.6 Missing Data**

In general, data will be analyzed as received from the clinical database. Hence, except for some partial/missing dates (see below), missing values, including those caused by dropouts, will not be imputed. Missing or partially missing dates in the following situations will be imputed for purposes of analysis:

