- A diagnostic, medical or surgical procedure (e.g., surgery, endoscopy, tooth extraction, transfusion). However, the medical condition for which the procedure was performed should be reported if it meets the definition of an adverse event. For example, an acute appendicitis that begins during the adverse event reporting period should be reported as the adverse event and the resulting appendectomy should be recorded in the subject's medical records and eCRFs.
- A pre-existing disease or condition or laboratory abnormality present or detected before the initial screening visit and that does not worsen.
- An intervention not associated with an untoward medical occurrence (e.g., hospitalization for elective surgery or for social and/or convenience reasons).
- An overdose without clinical sequela.

Verbatim terms of AEs will be mapped to preferred terms and related system organ classes (SOC) using the Medical Dictionary for Regulatory Activities (MedDRA) Version 16.1. The incidence rate of treatment emergent adverse events (TEAEs), defined as all adverse events reported as new or

worsened after the start of study drug, will be summarized by treatment group, system organ class, preferred term and maximum severity for all adverse events, serious adverse events, adverse events leading to discontinuation of study specified treatment, adverse events leading to discontinuation from the study and fatal adverse events using subjects in the safety population. In addition, summaries of exposure adjusted adverse event rates may also be presented. These summary tables will also be repeated for treatment related adverse events.

Tables will summarize the number and percentage of subjects having an event in each system organ class and preferred term by dose group. The denominator used to calculate incidence percentages consists of subjects receiving at least one dose of RX-0201 in the combination of RX-0201 and Everolimus group.

Further tables will summarize the number and percentage of subjects having adverse events, classified according to severity and the number and percentage of subjects with related events. The order of SOCs presented in tables will be according to the internationally agreed order of SOCs according to MedDRA. Within each SOC, the preferred terms will be shown in alphabetic order.

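### An adverse event with an unknown start day in the first-dose month is imputed to the 1st, so a new on-treatment event can be dated before dosing and drop out of the treatment-emergent tables

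*SAP*

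**What the plan says.** SAP 7.2.6 leaves missing values alone in general but makes an exception for dates: "Missing or partially missing dates in the following situations will be imputed for purposes of analysis". SAP 7.2.8 then deals with AE start dates in steps.

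- A query comes first: "For any adverse event that has a missing or incomplete start date, a query will be issued to capture the full date".
- Month and day both missing: "The date of the first dose of investigational product will be used as the start of the AE".
- Day only missing: "The year and month are reported (i.e., missing the day): The first day of the month will be imputed".

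Treatment-emergent status depends on timing. Protocol 9.5.2.1 describes TEAEs as "defined as all adverse events reported as new or worsened after the start of study drug", and SAP 8.10 uses the same definition. Pre-dose events have their own summary in Protocol 9.5.2.1: "The subject incidence rate of adverse events occurring between informed consent and first dose of study drug will be summarized".

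DLTs follow a different route. SAP 4.3, under Dose-Limiting Toxicity, says that the electronic data capture (EDC) "system will capture and identify whether or not a subject experiences a DLT in the AE dataset".

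**The concern.** The day-missing rule has no floor at the first dose. An event that began after dosing, in the same calendar month, receives an imputed start at the beginning of that month. If that date is earlier than the first dose, a new-onset event no longer meets the timing condition for a TEAE. It moves to the pre-dose summary, or to neither summary if the imputed date also precedes consent.

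The two neighbouring rules are also inconsistent. An event known only by its year is anchored to the first dose and keeps its TEAE status. The same event recorded more completely, with year and month, can lose it.

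At stake is the TEAE incidence in the early weeks of treatment. AE incidence is a secondary endpoint in both stages. For the day-missing rule, the error runs towards under-reporting.

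**Working it through.** The documents state no figure on this point, so there is none to reproduce. The check applies the rule as written.

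**Single case.** First dose 15 March 2017; AE truly begins 20 March 2017; recorded as March 2017 with no day.

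- Imputed start under SAP 7.2.8: 1 March 2017.
- Difference from first dose: 15 − 1 = 14 days before dosing, so the event is not treatment-emergent.

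The imputed date precedes dosing whenever the event falls in the first-dose month and the first dose was not on the 1st.

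**How often, given a missing day.** Inputs from the documents are the 21-day cycle and the planned 8 cycles (8 × 21 = 168 days). The assumptions, which are not in the documents, are that first-dose dates are uniform over the calendar, onset is uniform over the window, and every start day is missing after query.

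*By hand, for a 30-day month.* With the first dose on day d, the share of the 21 Cycle 1 days in the first-dose month is min(21, 31 − d)/21.

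- Days 1 to 10 each contribute 21, total 210. Days 11 to 30 contribute 20 down to 1, total 210.
- Mean over d = 1 to 30: 420/(30 × 21) = 420/630 = 0.667.
- A first dose on the 1st causes no misdating, so remove its 21 days: (420 − 21)/630 = 399/630 = 0.633.

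*By enumeration on the real calendar.* All 1,461 first-dose dates in a four-year span were used, with onset on each day of the window. An event counts as misdated if its imputed start is earlier than the first-dose date. Of all calendar days, 96.7% are not the 1st.

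| Window from first dose | Onset in first-dose month | Misdated before dosing | Misdated after the fix below |
|---|---|---|---|
| 21 days | 67.1% | 63.9% | 0% |
| 42 days | 37.5% | 35.1% | 0% |
| 168 days | 9.4% | 8.8% | 0% |

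The two methods agree for 21 days (63.3% and 63.9%). The share falls as the window lengthens because only the first-dose month is exposed.

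**The year-only rule.** It uses the first-dose date whatever year was reported.

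- Same year as first dose: the event is treatment-emergent, which is a reasonable default.
- Later year: the event stays treatment-emergent but is dated too early. This can happen, since 168 days of treatment can cross a year end and treatment beyond 8 cycles is allowed.
- Earlier year: an event known to precede treatment is made treatment-emergent.

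The anchor in this rule is the first dose of investigational product. Protocol 6 says RX-0201 is the only investigational product, and subjects randomized to everolimus alone never receive it (Protocol 7.5.3). For them the rule has no anchor date.

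**The case against.** Several limits on the harm stand.

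- **DLTs.** A reader might infer that the Stage 1 primary endpoint is at risk, because the exposed period overlaps the Cycle 1 DLT window. The documents do not support that. DLT status is flagged in EDC, and DLTs are reported on their own form within 24 hours of site awareness (Protocol 8.8). Neither depends on an imputed date.
- **Loss from the safety results.** A reader might infer that events vanish from safety reporting. They do not. All AEs are listed by subject (Protocol 9.5.2.1). The serious AE tables and the total, serious, related and Grade 3 and 4 listings in SAP 8.11 carry no treatment-emergent condition in their wording.
- **Size.** A reader might take 64% as the share of Cycle 1 AEs that are lost. It is a share of missing-day AEs only, in the least favourable window. Start date is a required item (Protocol 8.3), a query precedes imputation, and scheduled AE checks in Cycle 1 are about a week apart or closer. The number of dates left partial could be zero.
- **Direction.** The year-only rule mostly leans towards TEAE status. A pre-existing condition that does not worsen is not an AE (Protocol 8.1.1, SAP 8.10), so the earlier-year case should be rare.
- **The inference itself.** Neither document says outright that imputed dates decide TEAE status, and a pre-existing event recorded as worsened on treatment could still qualify.

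The last objection does not remove the point. Dates imputed for analysis, combined with a definition based on timing, lead to this result for a new-onset event. Neither document has a fallback that treats an AE as treatment-emergent unless its partial date shows otherwise.

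**Conclusion.** The day-missing rule is wrong as written. Unless dosing began on the 1st, it dates a new-onset, on-treatment AE in the first-dose month before dosing whenever the day is unknown after query. The harm is misclassification in the TEAE incidence tables.

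The rate of misdating is conditional: about 64% of missing-day AEs over 21 days, 35% over 42 days and 9% over 168 days, under uniform first-dose and onset dates. The number of partial dates is not in the documents, so the absolute effect cannot be stated. For scale, one affected subject with no other report of a term lowers its TEAE incidence by 1/20 = 5 points in a combination group of 20. That figure reflects group size and would follow from any one-subject change.

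The year-only rule is a lesser fault. It mistimes events from another year, generally in the conservative direction for TEAE counts.

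**What to change.** Amend SAP 7.2.8 before database lock.

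- **Day missing.** If the reported month and year equal those of the first dose of any study drug, impute the first-dose date, unless the AE end date shows that the event ended before dosing. Otherwise impute the 1st of the reported month.
- **Month and day missing.** If the year equals the first-dose year, impute the first-dose date. If it is later, impute 1 January of that year. If it is earlier, treat the event as pre-treatment.
- **Wording.** Refer to the first dose of any study drug, so that everolimus-alone subjects have an anchor. State that an imputed date equal to the first-dose date counts as on treatment, which is the convention used in the enumeration.

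The cost is a few lines of SAP text and programming. There is one small downside: a truly pre-dose AE in the first-dose month, with an unknown day and no end date to rule it out, may be counted as treatment-emergent. That is the conservative direction for safety.

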## **7.3 Interim Analyses and Data Monitoring**

### **7.3.1 Purpose of Interim Analyses**

Other than the safety evaluation required to determine whether to proceed to Stage 2 of accrual, no planned formal interim analysis will be performed.

If concerns arise during any data reviews, the sponsor may request additional specific safety data be collected and recommend modifying study conduct.

### **7.3.2 Planned Schedule of Interim Analyses**

As noted in Section 7.5.1, other than the safety evaluation required to determine whether to proceed to Stage 2 of accrual, no planned formal interim analysis will be performed.

### **7.3.3 Scope of Dose Escalation**

In the event that attribution of causality of potential DLTs to study drug may be equivocal, discussions with the investigators, medical monitor and sponsor will occur and additional subjects may be enrolled at that dose level. Reviews will be conducted by the investigators, medical monitor and sponsor of all available safety data on an ongoing basis throughout the study. The study sponsor or its designee will notify the sites when enrollment into a dose level is complete and when the next dose level is open to enrollment during Stage 1.

The establishment of the MTD or the safety of the target RX-0201 dose of 250 mg/m^2/day will be based on a review of the overall safety data by the investigators, medical monitor and sponsor. The MTD is the highest starting dose level associated with first-cycle DLTs in < 33.3% of subjects. Once the safety of the target RX-0201 dose of 250 mg/m^2/day is initially established, additional subjects (up to 20 subjects total) will be enrolled to receive RX-0201 at the target RX-0201 dose of 250 mg/m^2/day in Stage 2. Selection of a recommended Stage 2 starting dose from within the tested dose range will be based on evaluation of available safety information with findings regarding compliance.

#### **Stopping Rules**

The sponsor may also terminate the study at any time for reasons which may or may not be related to safety or study conduct.

### **7.3.4 Analysis Methods to Minimize Bias**

None.

### **7.3.5 Adjustment of Confidence Intervals and p-values**

Any statistical tests that are utilized will be two-sided, with a type 1 error rate of 5%. All confidence intervals will be two-sided, constructed at the 95% confidence level. Any inferential statistical tests conducted in this study will be considered exploratory in nature; therefore, no p-value adjustments for multiplicity analyses will be made.

Data will be summarized using the Safety Analysis Set with respect to enrollment and disposition summaries, demographics and baseline characteristics, concomitant medications, and safety measures. Summary (i.e. descriptive) statistics will include N, mean, standard deviation, median, range (minimum, maximum), values for continuous variables and frequencies, and percentages for categorical variables. Time-to-event analyses will be summarized using Kaplan-Meier survival analysis and graphs. 95% confidence intervals for the estimated median times and percentiles will also be displayed if applicable.

Missing or invalid data will be generally treated as missing, not imputed, unless otherwise stated (see Section 7.4).

### **7.3.6 Interim Analysis for Sample Size Adjustment**

Not applicable.

### **7.3.7 Practical Measures to Minimize Bias**

Not applicable.

### **7.3.8 Documentation of Interim Analyses**

Not applicable.

## **7.4 Multi-center Studies**

Up to 20 sites in the US will participate in this study. Sites that do not enroll subjects within 3 months of site initiation may be terminated.

Data from all centers will be combined for the analysis purposes.

## **7.5 Multiple Testing**

Not applicable.

# **8 Summary of Study Data**

## **8.1 Subject Disposition**

Subject enrollment by site and across all sites will be tabulated by dose group and all subjects.

The number of subjects discontinuing the study and the primary reason for discontinuation will be tabulated for descriptive purposes by dose group and overall.

Screen failure subjects will be included only in the disposition table and subject enrollment listing indicating reason for failure.

In addition, the number and percentage of subjects in each of the 4 analysis data sets (safety analysis set, full analysis set, per-protocol analysis set, and evaluable for tumor response analysis set,) will be summarized by treatment group.

## **8.2 Protocol Deviation**

A protocol deviation will be any noncompliance with the clinical trial protocol or Good Clinical Practice (GCP). The noncompliance may be either on the part of the subject, the investigator, or the study site staff. Protocol deviations will be identified and documented by Rexahn project management based on a review of data listings prior to database lock.

The number and percentage of subjects with any major and minor deviations will be tabulated for descriptive purposes by dose group and overall.

## **8.3 Demographic and Baseline Variables**

A summary of age, gender, race, ethnicity, metastatic clear cell renal carcinoma diagnosis, tumor stage, current disease status, time (months) from first diagnosis of metastatic disease to screening visit, prior medical history, prior anti-cancer systemic therapy (related to study indication), prior anti-cancer radiotherapy (related to study indication), prior anti-cancer surgery (related to study indication), vital signs at screening, and ECOG Performance Status will be presented using appropriate descriptive statistics by dose group. The categorical (discrete) variables will be summarized using counts and percentages. The continuous variables will be summarized using n, mean, median, standard deviation, and range (maximum, minimum).

## **8.4 Prior and Concomitant Medical Conditions**

The number and percentage of all subjects with any medical history will be summarized overall and for each body system. Body systems will be included as recorded on the eCRF. Percentages will be calculated based on number of subjects in the safety analysis set.

Subjects' medical history data including medical condition, start date and end date/ongoing will be presented in a listing.

## 8.5 Prior and Concomitant Medications / Non-Drug Treatments

For the purpose of this analysis, concomitant medications/therapies will be defined as those medications/therapies taken after the first administration of study drug; medications/therapies taken within 14 days prior to the first administration of study drug will be defined as prior medications/therapies. These medications will be coded using World Health Organization Drug Dictionary Enhanced (WHO Drug, June, 2014). The number and proportion of subjects in the safety analysis set using different prior/concomitant medications will be tabulated and summarized in a table by WHO Drug Anatomical-Therapeutic-Chemical (ATC) class and drug name for each dose group, and non-drug therapies will be mapped to preferred terms and related system organ classes (SOC) for each dose group. These data will also be presented in subject listings.

## 8.6 Treatment Compliance

Time on treatment (date of first dose to date of discontinuation date recorded on the end of study eCRF page) for each dose group will be characterized using descriptive summary statistics (n, mean, median, standard deviation, and range (maximum, minimum)).

$$\text{RX-0201 compliance at each visit (\%)} = \left[ \frac{\text{Total Actual Volume Administered (mL) of RX-0201}}{\text{Total reservoir volume of RX-0201}} \right] * 100$$

$$\text{Everolimus at each visit (\%)} = \left( \frac{\text{Number of Doses Taken}}{\text{Number of Expected Doses}} \right) * 100$$

A listing will be provided for the number and timing of prescribed dose reductions and dose interruptions.

## Safety Analyses

The incidence of subjects with adverse events and clinical laboratory abnormalities, defined as dose limiting toxicities after 1 cycle of therapy, is one of the primary endpoints. The safety of RX-0201 will be evaluated through reporting using the grading system in the CTCAE version 4.03 for adverse events and laboratory abnormalities. This will be used to grade changes in vital signs, and laboratory assessments to include serum chemistry, hematology, coagulation tests and urinalysis. All statistical methods for safety data will be descriptive in nature.

Dose Limiting Toxicities that occur during Cycle 1 will be tabulated by DLT criteria and RX-0201 dose level. Vital signs will be tabulated and presented as raw data and change from baseline at each time point. Laboratory safety data will be tabulated in shift tables based on laboratory-specific normal ranges. Adverse events will be tabulated by body system, intensity and relationship to study drug.

Vital signs, weight, and data will be summarized using appropriate descriptive statistics, by treatment group and time.

All subjects who receive at least 1 dose of RX-0201 will be included in the final summaries and listings of safety data. All safety analyses will be performed by dose level, treatment cycle, and week, where appropriate.

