##### Secondary objective(s):

- To assess the pharmacokinetics of RX-0201 in combination with everolimus (Stage 1)
- To evaluate parameters of clinical benefit of RX-0201 in combination with everolimus versus everolimus alone as measured by duration of response, time to response, and response rate (Stage 2)
- To evaluate the safety and tolerability of RX-0201 in combination with everolimus versus everolimus alone (Stage 1 and Stage 2)

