## **7 General Considerations**

The software used for all summary statistics and statistical analyses will be SAS Version 9.4 or later.

Safety, Efficacy, and PK assessments will be summarized separately for Stage 1 and Stage 2.

Additional summaries and analyses of pooled Phase 1 and 2 data may also be generated based on applicability of dosing regimens.

Unless otherwise noted, data will be summarized in tabular format by increasing dose level of RX-0201 for the combination of RX-0201 and Everolimus in Stage 1, by combination of RX-0201 and Everolimus in Stage 2, and by RX-0201 dose level for the combination of RX-0201 and Everolimus Stage 2. All groups combined (i.e., Total/Overall column) will also be presented when appropriate. All study data documented on the eCRFs will be included in the study data listings.

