### **7.2.3 Safety Analysis Set**

The safety analysis set includes all subjects who receive at least one dose of study drug(s) with subjects analyzed according to the treatment received. All safety data will be analyzed in accordance with this analysis set. The safety analysis set will be defined as all subjects who receive at least 1 dose of study drug. These subjects will be analyzed according to the treatment received. All safety data will be analyzed in the safety analysis set.

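### SAP 8.10's adverse-event denominator and the default table columns leave the three everolimus-only subjects out of the safety summary tables, contrary to the SAP's own Safety Analysis Set

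*SAP*

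**What the plan says.** Two sets of statements in the SAP do not fit together.

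The general rule is in SAP 7.2.3: "The safety analysis set includes all subjects who receive at least one dose of study drug(s) with subjects analyzed according to the treatment received". It continues: "All safety data will be analyzed in accordance with this analysis set". Protocol 9.2.2 gives the same definition, and SAP 7.3.5 again names this set for safety measures. The secondary objective in SAP 4.1 is "To evaluate the safety and tolerability of RX-0201 in combination with everolimus versus everolimus alone".

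The working instructions are narrower:

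- Safety Analyses text, after SAP 8.6: "All subjects who receive at least 1 dose of RX-0201 will be included in the final summaries and listings of safety data".
- SAP 8.10: "The denominator used to calculate incidence percentages consists of subjects receiving at least one dose of RX-0201"; the sentence goes on to limit this to the combination group.
- SAP 7, on the Stage 2 table columns: "by combination of RX-0201 and Everolimus in Stage 2, and by RX-0201 dose level". An overall column may be added, but no everolimus-alone column is listed.

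Just before the denominator sentence, SAP 8.10 also says that treatment-emergent AEs are summarised by treatment group in the safety population. The section therefore gives two rules for the same tables.

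**The concern.** Protocol 3.3 and SAP 6 count 3 Stage 2 subjects on everolimus alone, and Protocol 7.5.3 says they receive no RX-0201. A rule that depends on receiving RX-0201 cannot count them. If 8.10 and the SAP 7 columns are programmed as written, these subjects have no AE column and no denominator, and the comparison named in the objective has nothing on one side. Two programmers could also produce different Stage 2 and overall AE percentages from the same SAP.

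The omission does not look deliberate. Protocol 9.5.1 requires changes from its analyses to be described in the SAP, and SAP 11 lists none. After randomization stopped, the protocol kept AE, vital-sign and compliance collection for these subjects (Protocol 7.5.4 and 7.5.5; Appendix B, note 18). SAP 9.1.1 still plots their progression-free survival and runs a log-rank test against them.

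**Working it through.** This is a question of who is counted, so no power or error-rate formula applies.

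**Inputs**
- Stage 1: about 9 subjects, all assigned RX-0201 (SAP 6)
- Stage 2 everolimus alone: 3 (Protocol 3.3; SAP 6)
- Stage 2 combination: up to 20 (same places)
- Planned total: about 32 (SAP 6)

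**The plan's own total.** 9 + 3 + 20 = 32, which matches SAP 6.

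**Denominators under the two rules**, assuming every planned subject is dosed and every combination subject starts RX-0201:

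| Group | Safety Analysis Set | RX-0201 recipients | Difference |
|---|---|---|---|
| Overall | 32 | 9 + 20 = 29 | 3/32 = 9.4% |
| Stage 2 | 23 | 20 | 3/23 = 13.0% |
| Everolimus alone | 3 | 0 | no percentage can be computed |

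Protocol 2.3.2 reports 10 subjects treated in Stage 1 (3 + 4 + 3). On that count the overall figures are 33 against 30, and 3/33 = 9.1%.

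**Effect on a pooled Stage 2 percentage.** Assume, for illustration, that 10 of 20 combination subjects have an event and y of the 3 everolimus-only subjects do, with y from 0 to 3:
- Safety Analysis Set: (10 + y)/23, from 43.5% to 56.5%.
- RX-0201 recipients only: 10/20 = 50.0% whatever y is.
- Everolimus-only events kept in the numerator over the RX-0201 denominator: (10 + y)/20, from 50% to 65%.

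**What three subjects can show.** With 0 events in 3, the exact two-sided 95% upper limit is 1 − 0.025^(1/3) = 70.8%, so the interval is 0% to 70.8%.

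**Where the subjects still appear.** SAP 7 puts all data recorded on the eCRFs in the listings. SAP 8.11 lists deaths on study and serious AEs without an RX-0201 condition. Protocol 9.5.2.1 lists every AE by subject and provides narratives for serious and fatal events. The gap is therefore in the summary tables and percentages. The mention of listings in the Safety Analyses sentence does not match SAP 7 and needs aligning.

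**The case against.** The best defence is that nothing in the SAP expressly excludes these subjects. The Safety Analyses sentence says that RX-0201 recipients are included; it does not say that only they are. The denominator sentence follows tables described by dose group and names the combination group, so it may define the denominator for the combination columns alone. The SAP 7 columns are a default, and SAP 8.14.2 summarises vital signs by treatment group. Much of this stands: the exclusion is the literal result of conflicting text, not a settled intention. But if the denominator sentence covers only the combination columns, the everolimus-alone group has no stated denominator and still no default column. Wording is needed on either reading.

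A second defence is that study drug may mean RX-0201 alone, since Protocol 6 calls it the only investigational product. This is weak. Protocol 6.1, on study drug administration, opens with everolimus dosing, and both set definitions allow for more than one drug and analyse by treatment received.

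A third is that the everolimus arm was closed by amendment and three subjects show little. That is correct and limits the severity, but it does not justify leaving treated subjects out of a descriptive table.

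A reader might go further and infer that serious events and deaths in these subjects would be missing from the report. The documents do not support that, given the listing and narrative provisions in SAP 7, SAP 8.11 and Protocol 9.5.2.1. A combination subject who took everolimus but never started the infusion would also be lost under the RX-0201 rule. Both drugs are scheduled for Cycle 1 Day 1, however, and the documents give no count, so that case is hypothetical.

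**Conclusion.** The point holds for the summary tables. The denominator rule in SAP 8.10, the Safety Analyses text and the SAP 7 columns contradict the Safety Analysis Set, 8.10's own statement on the safety population, and the safety objective. Taken literally, they remove 3 subjects from the AE tables and percentages: 13% of Stage 2 and 9.4% of the planned total. This rests on the planned group sizes and on study drug including everolimus. It should be fixed but is not a must-fix. The safety methods are descriptive, three subjects support no inferential comparison with or without the column, and neither primary endpoint (Stage 1 dose-limiting toxicity, Stage 2 progression-free survival) is affected.

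**What to change.** Before database lock:

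1. In the Safety Analyses text and in SAP 8.10, replace the RX-0201 condition with the Safety Analysis Set, stated as any dose of RX-0201 or everolimus, by treatment received. This also settles whether study drug includes everolimus.
2. In SAP 7, add a descriptive everolimus-alone column (planned n = 3) to the Stage 2 safety tables.
3. Use each column's own Safety Analysis Set count as its denominator, with any overall column covering all dosed subjects in the groups it combines.
4. Align the listing wording in the Safety Analyses text with SAP 7, so that listings cover all subjects.

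The cost is a few sentences and one table column. No new data are needed, because the protocol already collects safety data on these subjects.
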